identified locations. All data collection activities will comply with the recommended social distancing requirements currently in place at the time.

Quantitative study measures will be implemented through the use of on-line REDCAP survey software and is available to interested individuals through an on-line link. Participants can complete the survey in any environment in which they have access to the Internet (i.e., public library; home; work). If the interested participant does not have a device to access the Internet and the survey or communicate with the researcher to indicate their responses, the primary researcher will meet them a place identified as convenient for the participant with the necessary equipment to complete the survey (i.e., laptop computer with Internet connectivity).

8) Prior Approvals

N/A

9) Study Design

Recruitment Methods

Recruitment will occur through local community partners, which include Philadelphia Independence Network, Community Integrated Services, Carousel Connection GRASP, ASERT, Philadelphia the Institute of Disability at Temple University, and the Philadelphia Area Charter School. We have an established relationship with all of these organizations. An introductory recruitment e-mail (see materials submitted with IRB protocol) will be sent to potential participants through the organization, which includes a link to the survey questions on REDCAP.

Phase 1

We intend to recruit 20 employed individuals with ASD and 20 employed individuals with IDD to complete in depth qualitative interviews, 100 employed individuals with ASD and 100 employed with IDD to complete **quantitative** perceptual mapping surveys. We will recruit 40 individuals 10 ASD 10 IDD, 10 vocational staff, and 10 from the project Advisory Board to conduct vector modeling analysis with and complete sample messaging. We aim to recruit at least 120 participants with ASD and 120 participants with IDD for the pilot SAFE program, which we anticipate will yield a total of 96 participants in the final sample when accounting for 20% attrition rates commonly identified in prior intervention studies of people with ASD and/or IDD.

Phase 2

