We intend to complete the **SAFE program** and interviews over the course of three years starting as soon as IRB approval is obtained. We intend to complete the qualitative interviews and quantitative surveys in the first year. We intend to implement the SAFE program until approximately 120 participants have completed the program and data collection during year two and three. Recruitment will occur throughout the course of the study until the targeted number of participants is obtained. We will use block randomization, which will allow us to have continuous enrollment in the study.

Participation in the **SAFE program** is completed over the course of 2-4 weeks.

Participants will meet 2-3 times a week for approximately 60 minutes with either staff, a peer support specialist peer, or occupational therapy graduate students. The meetings will provide direct instruction and role play experiences covering the main concepts and proper use of preventable behaviors to protect against COVID-19 and other airborne diseases in the workplace.

Phase 2

Phase 2 will be completed over the course of one year following IRB approval. During the first two months, recruitment for the focus groups will take place. In months 2-4, focus groups will be conducted, and their feedback will be analyzed. Months 4-8 will involve revising the SAFE curriculum by adding lessons based on the focus group feedback. The final months will focus on recruitment and training.

Study Procedures and Data Analysis

Procedures.

To assess perceptions of peer-support interventions and use of preventative decision-making practices for individuals with ASD and or IDD in the workplace we will conduct in-depth qualitative interviews with individuals with ASD and or IDD working 10 hours or more a week (n=20 or until data saturation) who receive employment services or supports in order to: 1) understand the barriers and facilitators of implementing preventative decision-making practices for IADs and individuals with IDD in the workplace; 2) examine the perceptions and acceptability of peer support intervention strategies; and 3) develop a perceptual mapping survey instrument based on these findings.

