If the participant is assigned to the staff intervention support staff will be contacted with an email or phone call. Staff members will be required to complete human subjects training. Researchers will obtain informed consent for all participants. During the first contact made with participants, written information will be provided remotely using Zoom/FaceTime or in person to all participants explaining the following in simple terms: 1) the criteria for participation, 2) the purpose of the research and the procedures involved, 3) the subject's right to withdraw at any time without penalty of any sort, 4) potential benefits to the subject, 5) potential risks, 6) assurance of anonymity, and 7) terms of remuneration. All research staff will complete training about the informed consent process prior to consenting subjects. The information described above will be reviewed and any questions answered. Participants will be obtained signed or a printed signature box used for signature when electronic signatures are unable to be obtained for consent either in person or virtually.

We will collect data from young adults or transitional aged-youth with ASD or IDD to determine the efficacy and feasibility of the intervention. Recruitment occurs through the sites identified in the participant recruitment section of this proposal. Participants interested in the study will contact the primary investigator or research staff who will schedule an initial physical or virtual meeting at a place and time convenient for the participant to determine inclusion and obtain consent/assent. Participants are randomly assigned to either peer-support intervention, staff intervention or a control group. We will randomize in blocks of 12 (4 to each group) until we reach the targeted number of 120 or

SAFE Protocol

40 participants in each group. Pre-test and post-test measures will be administered by researcher staff prior to the start of the intervention (Pre-test) and at the end of the intervention 4 weeks (Post-test). Key stakeholders, including the participants and interventionists (occupational therapists and peer mediators), will complete qualitative interviews at the end of the intervention period for each participant. The information gathered will determine acceptability and feasibility of intervention. Participants will be asked to discuss their experiences during the intervention specific to their assigned intervention group.

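### The protocol fixes one block size of 12 and specifies neither allocation concealment nor any use of ASD/IDD diagnosis in the randomisation or the ANOVA

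*Combined protocol and SAP*

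**What the plan says.** **Allocation.** Under Procedures in section 9, "Participants are randomly assigned to either peer-support intervention, staff intervention or a control group". The block rule follows: "We will randomize in blocks of 12 (4 to each group"), up to a total of 120, or "40 participants in each group". Study Timelines (9b) gives the reason for blocking: "We will use block randomization, which will allow us to have continuous enrollment in the study". No other block size, sequence generator, list holder or concealment method is given.

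**Who enrols, and what they can see.** "Participants interested in the study will contact the primary investigator or research staff who will schedule an initial physical or virtual meeting", and that meeting settles inclusion and consent. The Inclusion and Exclusion Criteria (9a) leave adequacy of communication skills to be judged at the initial meeting. The arms look different once assigned. "If the participant is assigned to the staff intervention support staff will be contacted with an email or phone call", and controls simply keep their usual vocational supports. Research staff administer the pre-test and post-test. Blinding is not mentioned.

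**Diagnosis.** Recruitment Methods, Phase 1, sets a target of "120 participants with ASD and 120 participants with IDD for the pilot SAFE program", whereas 9a, 9b and Procedures work to 120 in total. No stratification factor is named. Diagnosis is recorded at pre-test under Demographics and Potential Moderators, but the Data Analysis paragraph, which plans ANOVAs within and between groups, names no diagnosis term.

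**The concern.** Two separate matters arise from the same short allocation paragraph.

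The first is predictability. Anyone who knows the block size and the assignments already made can work out the last place in each block, and sometimes earlier places. Inclusion rests partly on a judgement, so a person who knows the next arm could, even unintentionally, influence who enters it. Concealment exists to prevent this, and the plan does not describe any.

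The second is balance. The trial takes in two diagnostic groups that may differ in level and in response. If neither the randomisation nor the analysis uses diagnosis, the arms may differ by chance in their ASD share and the variation due to diagnosis stays in the error term. The peer-versus-staff comparison, the third research question, is the one most likely to involve a small difference and so to suffer from lost precision.

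**Working it through.** **Inputs.** From Procedures: block of 12, three arms, 4 per arm, total 120, 40 per arm. Assumed, because the documents do not give them: an enroller who knows the block size and every earlier assignment (for predictability), and a 60/60 ASD/IDD mix with no stratification (for balance).

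**1. The plan's own figures.** 120 / 12 = 10 blocks, and 10 × 4 = 40 per arm. These reproduce.

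**2. Assignments certain in advance.** With j places left in a block, the next assignment is certain if all j belong to one arm. The probability is 3 × C(4,j) / C(12,j):
- j = 1: 3 × 4/12 = 1.000
- j = 2: 3 × 6/66 = 0.273
- j = 3: 3 × 4/220 = 0.055
- j = 4: 3 × 1/495 = 0.006

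The sum is 1.33 per block. That is 1.33/12 = 11.1% of assignments, or 13.3 of 120.

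**3. Partial knowledge.** At least one arm can be ruled out when it is absent from the remaining places. Summing 3 × C(8,j)/C(12,j) − 3 × C(4,j)/C(12,j) over j gives 3 × 8/5 − 3 × 4/9 = 4.80 − 1.33 = 3.47 per block (28.9%, about 35 of 120), including the certain ones. Always guessing the arm with most places left is right 51.2% of the time, against 33.3% by chance (recursion over all blocks).

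**4. Other block schemes.** A smaller fixed block is worse: 14.3% of assignments are certain at size 9 and 20.0% at size 6. With sizes 9, 12 and 15 chosen at random, an observer who knows those three sizes and tracks every consistent state is certain of about 1.8% (simulation).

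**5. ASD share, peer versus staff.** Let D be the difference in ASD counts between two arms of 40. Without stratification, Var(D) = 2 × 40 × 0.5 × 0.5 × 120/119 = 20.2, so SD = 4.49 people. The median of |D| is about 0.674 × 4.49 = 3 people, and 3/40 = 7.5 points. A gap of 20 points is 8 of 40. With continuity correction, 7.5/4.49 = 1.67, which gives about 9%. Exact enumeration agrees.

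**6. ASD share, highest versus lowest of three arms.** The arm counts a, b, c have probability C(40,a) C(40,b) C(40,c) / C(120,60), with a + b + c = 60. The median range is 5 people (5/40 = 12.5 points). A range of 8 or more has probability 22%.

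**7. Sensitivity to the assumed mix and total.** With 30 ASD and 90 IDD, a gap of 8 or more occurs in 13% of lists across three arms and in 5% for one pair. If 240 are randomised (120 + 120, 80 per arm), the three-arm gap is 10 or more people (10/80 = 12.5 points) in 29% of lists. The same enumeration with 80 in place of 40 gives 20 points (16 of 80) or more in about 4%.

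**The case against.** A block of 12 is conventional and fairly large for three arms. Even a fully informed observer is certain of only about one assignment in nine, so varying the size is a refinement. This stands, and it limits the size of the point.

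A reader might infer that enrolling staff do see earlier assignments, or that there is no concealment. The documents do not support this. They do not say who holds the list or who learns the assignments, and a method that is not described is not thereby absent. The 11% is therefore conditional.

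A reader might also infer a single pooled list. The one target of 120 fits that, but blocks of 12 fit separate lists as well: 60/60 is 5 blocks each, and 120 + 120 is 10 each. What can be said is that stratification by diagnosis is not specified.

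Chance imbalance does not bias a randomised comparison in expectation. Outcomes are also measured before and after. If the ANOVAs analyse change or repeated measures, stable differences in level between ASD and IDD largely cancel, and mainly different change by diagnosis remains. The ANOVA model is not stated closely enough to rely on this, but the argument has force.

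Finally, the randomised comparison belongs to Phase 1, and Phase 2 has no pilot with participants. Enrolment may be complete, in which case changes to the list come too late. The documents do not give enrolment status.

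**Conclusion.** The point holds as a modest gap in specification. The plan fixes and discloses one block size, the arms are evident after assignment, inclusion involves judgement, and neither concealment nor stratification by diagnosis is specified. If enrollers know earlier assignments, about 11% (13 of 120) are certain in advance. If allocation is unstratified and the mix is 60/60, a 20-point gap in ASD share arises in 22% of lists across the three arms, and in about 9% for peer versus staff, the contrast that matters most. With a 30/90 mix these fall to 13% and 5%. The consequence of imbalance is lost precision and possible confounding in the one sample obtained.

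It would go too far to conclude that selection bias has occurred or that the randomised comparison is invalid. Nothing in the documents shows that foreknowledge existed or was used.

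**What to change.** 1. **Whatever the enrolment status:** include diagnosis as a factor in the ANOVA and say so in Data Analysis. It is already collected, so the cost is one sentence and one model term. State also how assignments were, or will be, concealed and who holds the list.
2. **Reconcile the target first.** Recruitment Methods gives 120 + 120; 9a, 9b and Procedures give 120 in total. This sets the number of lists and blocks.
3. **For participants still to be randomised:** choose block sizes at random (for example 9, 12 and 15) and keep them out of staff-facing documents. Release each assignment only after consent and pre-test. REDCap, already used for surveys and consent, could hold the list.
4. **Stratify those participants by primary diagnosis,** with a written rule for people who have both ASD and IDD. The protocol often writes ASD and/or IDD, diagnosis is self-reported, and other diagnoses are recorded, so the two strata are not separate without such a rule.

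The cost of items 3 and 4 is a new list for the remaining participants. The downside is that arm sizes may end a few apart instead of exactly 40 each.

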A member from the research team will then contact interested individuals to set up a convenient meeting time and place for the **SAFE** program training. These meetings will occur remotely or in a private location convenient to the participant. The **SAFE** program course training will occur in small group settings or individually. The course trainings will occur 2-3 times per week for between 45-60 minutes. An appropriate curriculum has been developed by Temple University Researchers and Occupational therapy students based on many qualitative interviews, research of proper education methods, and COVID-19 practices. The curriculum is based on a series of classes designed to create an understanding of best practices and behaviors to prevent the spread of COVID-19 in the workplace. The curriculum will be adapted to meet the needs of this project and study population. The course will provide instruction in the following areas: 1) COVID-19 and how it spreads 2) PPE and How to use it properly 3) Social Distancing 4) Community Participation 5) Employment 6) Self Efficacy.

Participants will complete the **SAFE** program sessions remotely or in person in a private, quiet and convenient setting.. Participants will be randomized into two treatment arms and a control group. The first treatment arm will receive the **SAFE** program implemented through a staff training model. The second group will receive the program using a peer support model. The control group will continue to receive their standard vocational rehabilitation supports.

Training of the **SAFE** program will occur remotely or person by staff who are trained within our research team or we will implement it in collaboration with staff or a peer specialist remotely as part of their current services. If it is in person it will be implemented at their vocational rehabilitation centers or places of employment. Research staff will be available to support the process after the training is complete.

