review codes, 2) identify areas of disagreement, 3) recode data until consensus is reached, and 4) collapse initial codes into a preliminary framework of interrelated themes. The transcripts will be reanalyzed until a final thematic structure is reached. The research team will implement a number of methodological actions to strengthen the data collection process and trustworthiness including reflexivity, triangulation, and stakeholder checks.

Demographics and Potential Moderators.

The research team, primary investigators or research assistant, will collect demographic data including age, gender, ethnicity, education, type of area lived in, and primary and other diagnosis. The demographic form is completed *only* during pre-test data collection. Additionally, we will track participants who acquire an infectious airborne disease (IAD) during the course of participation in the study. This is not considered a primary outcome as we are not able to incorporate contact tracing within the scope of this project. Therefore, it is unlikely that we can confidently identify whether the participant acquired the IAD in the workplace. We will rely on self or caregiver report to acquire this information. The process of collecting this information will help in determining if it is feasible to include this as an outcome in future research.

Primary Outcomes Measure will be collected by the research team, primary investigators or research assistant.

Workplace Health and Safety Assessment. The Workplace Health and Safety Assessment assesses *both* knowledge and actionable behaviors participants exhibit to prevent IADs. The items for the tool were developed from recommendations provided by the CDC to reduce exposure to IADs including use of personal protective equipment, personal hygiene and social distancing. The assessment includes 20 items and takes approximately 15-20 minutes to complete through both administrator observations in the workplace environment (8 items) and questions completed by the participant (12 items). Response options are “rarely, never, sometimes, most of the time, always” and are scaled from 1 to 5 respectively. A total raw score is provided for data analysis.

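### Eight of the 20 items of the first-listed primary outcome are scored by the research team's observation, with no masking and no rule separating a participant's rater from that participant's trainer

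*Combined protocol and SAP*

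**What the plan says.** All references are to section 9 of the combined protocol and SAP.

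- **The outcome.** The Workplace Health and Safety Assessment comes first under the primary outcomes (Measures). "The assessment includes 20 items", completed "through both administrator observations in the workplace environment (8 items) and questions completed by the participant (12 items" in number). Responses "and are scaled from 1 to 5 respectively". For the analysis, "A total raw score is provided for data analysis"; no separate observed score is planned.
- **Who rates.** "Primary Outcomes Measure will be collected by the research team, primary investigators or research assistant" (Measures). Under Procedures, "Pre-test and post-test measures will be administered by researcher staff prior to the start of the intervention (Pre-test"), and again at the end of the intervention at 4 weeks.
- **Who delivers SAFE.** Procedures names "staff who are trained within our research team", and alternatively has the team implement the program jointly with agency staff or a peer specialist. Study Timelines names staff, a peer specialist or occupational therapy graduate students.
- **What else happens around post-test.** Procedures has participants interviewed at the end of the intervention about the arm they were in. The qualitative data collection paragraph gives interviewing to a primary investigator, research assistant or occupational therapy student. The Feasibility Data paragraph has participants complete the Acceptability of Intervention Measure (AIM) at the first post-test.
- **What is absent.** Nothing in the document mentions blinding, an independent assessor, or a rule on who may rate whom.

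**The concern.** An observer who scores behaviour on a five-point frequency scale has room for judgement. If that observer knows the participant was taught SAFE, or did the teaching, scores can drift upward in the SAFE arms and not in the control arm. That would look like a treatment effect.

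The 12 participant-answered items are open to self-report bias whatever is done, because participants know what they received. The 8 observed items are the part where masking could help. The abstract promises to examine observable preventative behaviours, so a reader will give these items weight. Once all 20 are summed, the reader cannot tell which source produced a difference.

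**Working it through.** **1. Share of the score.** Items: 8/20 = 40%. Each item runs from 1 to 5, a span of 4 points. The total spans 20 × 4 = 80 points and the observed part 8 × 4 = 32 points; 32/80 = 40%.

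**2. Sample size.** The inclusion criteria give 120 recruited and 20% attrition: 120 × 0.80 = 96, which reproduces the plan's figure. With equal allocation (blocks of 12, 4 to each group), 96/3 = 32 per arm.

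**3. Can the rater learn the arm, or be the trainer?** Setting the passages side by side:

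| Task | Roles named |
|---|---|
| Collect primary outcomes | research team, primary investigators, research assistant |
| Conduct interviews | primary investigator, research assistant, occupational therapy student |
| Deliver SAFE | staff trained within the team, the team jointly with agency staff or a peer, occupational therapy students |

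Investigators and research assistants appear in both of the first two rows, and the end-of-intervention interview is about the assigned arm. The AIM asks about an intervention that the control group does not receive, so handling it can reveal the arm at the same time point. Knowledge of the arm at post-test is therefore likely, though not stated. At pre-test the inference is weaker: SAFE has not started, and the plan does not say whether randomization comes first. Bias at post-test alone is enough to distort change from baseline. Overlap of rater and trainer is possible, because the team itself may take part in delivery.

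**4. Illustration of size.** The plan states no SD, alpha, power or rater shift, so these inputs are assumptions: no true effect, two-sided 0.05, SD of the total 8 to 15, and a lift of b points on each observed item in the SAFE arms.

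- Shift in the total = 8 × b: 0.8, 2.0 and 4.0 points for b = 0.1, 0.25 and 0.5.
- SE of one SAFE arm against control = SD × √(2/32) = 0.25 × SD.
- With δ = shift/SE, the chance of a false significant result = Φ(δ − 1.96) + Φ(−δ − 1.96).
- Example, SD 8 and b = 0.25: SE = 2.0, δ = 1.0, Φ(−0.96) + Φ(−2.96) = 17.0%.

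| Assumed SD | b = 0.1 | b = 0.25 | b = 0.5 |
|---|---|---|---|
| 8 | 6.9% | 17.0% | 51.6% |
| 10 | 6.2% | 12.6% | 36.0% |
| 12 | 5.8% | 10.2% | 26.6% |
| 15 | 5.5% | 8.3% | 18.7% |

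The plan names ANOVA, so I also checked the three-arm omnibus test with both SAFE arms lifted equally. With e = shift/SD, the noncentrality is 32 × (2/3) × e² on 2 and 93 degrees of freedom. For b = 0.25 this gives 15.9% at SD 8 and 7.9% at SD 15, close to the pairwise figures.

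**5. Which contrast is affected.** An equal lift in both SAFE arms moves SAFE against control. It cancels in peer against staff, which is research question 3.

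**The case against.** The strongest reply is that the documents are silent rather than incriminating.

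- **Knowledge of the arm.** A reader might infer that the raters know the arm. No passage says so; silence supports only that masking is not provided for. This stands. The sentence assigning interviewers also sits in a paragraph that times interviews before the end of SAFE, so applying it to the exit interview is itself an inference, though no other interviewers are named.
- **Trainers rating their own trainees.** A reader might infer this too. The phrase "staff who are trained within our research team" can mean agency staff whom the team has trained, and Procedures names occupational therapists and peer mediators as interventionists. The named roles largely differ. This stands in part: joint implementation by the team keeps overlap possible, and nothing forbids it.
- **Only evidence of behaviour.** It would be wrong to call the 8 items the trial's only behavioural evidence. The VocFit Safety Subscale covers demonstrated safety ability, and the self-advocacy scale is reported by staff as well as by participants. The plan does not say who rates the VocFit, however, and masks neither measure.
- **Size.** The false-positive figures depend on assumed SDs and lifts. This stands, and is why a range of both is shown.
- **Subtotals.** A true behaviour effect and a rater effect would both appear in the observed items, so subtotals cannot tell them apart. This stands; they show only which source drives a result.

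**Conclusion.** The concern holds as a gap in the plan. Followed as written, the plan lets research-team members score 8 of 20 items of the first-listed primary outcome without masking and without separation from delivery, at a time point when the arm is likely to become known. The exposed part is 40% of the score range, and the exposed comparison is SAFE against control.

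The consequence could be small or large: about 5.5% to 7% false positives instead of 5% for a lift of 0.1 point per item, and 19% to 52% for 0.5 point, over an assumed SD of 8 to 15 with 32 per arm. These figures show direction and plausible scale. They do not estimate a bias that has occurred, and the documents do not establish that any rater is unmasked or rates a participant whom they trained. This is a correctable weakness that should be addressed, not a fatal flaw.

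**What to change.** In section 9, in the Procedures paragraph on pre-test and post-test and in the Workplace Health and Safety Assessment entry under Measures, state that the post-test workplace observation is done by an existing research-team member who:

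- did not deliver SAFE to that participant;
- is not told the arm;
- completes the 8 items before the AIM and the exit interview, which someone else handles.

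Record any accidental unmasking. Some is to be expected, since in-person SAFE may be delivered at the place of employment where the observation is made.

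Report the 8-item observed subtotal and the 12-item participant subtotal beside the total, with a note that the subtotals do not by themselves detect observer bias. Where post-tests are already complete, the subtotals can still be computed if item scores were kept.

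The cost is some scheduling constraint and one extra table. The plan names several team roles, so reassignment within the team looks feasible, but it does not give the team's size and the sponsor should confirm this.

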Based on the feedback received, research staff will make any necessary revisions to ensure the materials are both effective and accessible.

Once finalized, the new content will be integrated into the existing SAFE program materials. Research staff will adapt the content into various formats, including written guides, videos, and infographics, to meet the diverse learning needs of participants.

Pilot Testing for Service Providers

- Research staff will recruit 5-10 staff members from a large service provider organization to participate in pilot testing of the training materials. This pilot testing will occur over a 1-2 month period, during which staff will be trained on the new SAFE materials and additional content. The trainings will occur using Zoom meetings. The training sessions will be conducted either in groups or individually, depending on scheduling availability. Feedback will be collected from participants through surveys, interviews, or debriefing sessions to evaluate the effectiveness of the training. The training feedback will be audio recorded to ensure that we capture all important information you share. The audio recordings will be transcribed by the project team using Zoom's transcription feature. By signing the consent form, you are giving permission to be recorded.
 - Only people working on this project will have access to the recordings.
 - Information and transcripts will be stored securely in locked filing cabinets or on password-protected computers.

Based on this feedback, research staff will refine the training materials and curriculum, making necessary adjustments to improve clarity, accessibility, and applicability. These

SAFE Protocol

trainings will not be recorded. Feedback will only be collected using FIM surveys, AIM surveys and exit interview.

Once these refinements are complete, the finalized curriculum will be prepared for broader implementation within service-based organizations that support individuals with IDD. Participants will receive \$50 for the training. Participant will receive \$25 after the first training sessions and an additional \$25 after completion.

Data Analysis. Descriptive statistics including mean, median, standard deviation, skewness, frequencies, and percentages will be computed on demographic and measures as appropriate. We will complete ANOVAs to determine if there were significant changes in scores on outcome measures within and between groups. We will use SPSS to complete the analyses.

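### The planned ANOVA has no term for shared SAFE training groups or arm-specific facilitators, so peer-vs-staff standard errors are too small if sharing occurs and outcomes within clusters are positively correlated

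*Combined protocol and SAP*

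**What the plan says.** All references are to the combined protocol and SAP.

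- **Allocation** (Study Procedures and Data Analysis, Procedures): individuals are randomised to three arms: "We will randomize in blocks of 12 (4 to each group"), up to 120 in total, or 40 per arm. Section 9(b), Study Timelines, adds: "We will use block randomization, which will allow us to have continuous enrollment in the study".
- **Delivery format** (Procedures): the SAFE "program course training will occur in small group settings or individually". The number and size of groups, and the share of participants taught individually, are not given.
- **Who delivers**: section 9(b) lists "either staff, a peer support specialist peer, or occupational therapy graduate students". Procedures describes delivery by "staff who are trained within our research team or we will implement it in collaboration with staff or a peer specialist remotely". One SAFE arm follows a staff model and the other a peer model, while controls keep their usual vocational supports. Procedures also says: "If the participant is assigned to the staff intervention support staff will be contacted with an email or phone call".
- **Analysis** (Data Analysis): "We will complete ANOVAs to determine if there were significant changes in scores on outcome measures within and between groups". Beyond descriptive statistics, this is the whole quantitative plan for the outcome measures. It has no group or facilitator term, robust standard error, ICC or design effect.
- **Objective** (section 5): research question 3 asks whether peer delivery gives a larger gain than staff delivery.

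**The concern.** People taught together, or by the same person, tend to finish more alike than people who are not. Individual randomisation does not remove that similarity, because it arises after allocation through delivery. An ANOVA on individual scores counts each person as a separate piece of evidence.

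The peer-vs-staff question is the most exposed. Peers belong to one SAFE arm and staff to the other, so differences between individual facilitators are part of the noise in that comparison. If they are left out, one unusually good peer or staff member can look like an effect of the delivery model, with a p-value that is too small and an interval that is too narrow. A SAFE-vs-control comparison is affected by any sharing in the SAFE arm, though less, because controls are unclustered.

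**Working it through.** **1. The plan's own figure.** Section 9(a) plans for 20% attrition: 96/(1 − 0.20) = 120 enrolled, so 96/3 = 32 completers per arm. This reproduces exactly. It contains no allowance for clustering, and no power calculation is stated.

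**2. Formulas.** For equal clusters of size m nested in both SAFE arms:
- design effect DE = 1 + (m − 1) × ICC
- true SE / ANOVA SE ≈ √DE
- actual type I error ≈ 2 × [1 − Φ(1.96/√DE)]

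The ICC is that of the score analysed (for example the change score). m, the ICC and a two-sided 5% level are assumptions.

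Example, m = 4 and ICC 0.05: DE = 1 + 3 × 0.05 = 1.15; √1.15 = 1.07; error ≈ 6.8%.

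**3. Simulation.** Three arms of 32, pooled three-arm error (93 df), peer vs staff, both SAFE arms fully nested:

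| Cluster size | DE at ICC 0.01 / 0.05 / 0.10 | Actual error of a nominal 5% test |
|---|---|---|
| 1 (nothing shared) | 1.00 / 1.00 / 1.00 | 5.0% throughout |
| 2 | 1.01 / 1.05 / 1.10 | about 5 / 5.6 / 6% |
| 4 | 1.03 / 1.15 / 1.30 | 5.3 / 6.7 / 8.7% |
| 8 | 1.07 / 1.35 / 1.70 | 5.9 / 9.2 / 13.3% |

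Variants, at the same three ICCs:
- Half of each SAFE arm sharing: 5.2 / 6.0 / 6.8% (clusters of 4) and 5.4 / 7.0 / 9.3% (clusters of 8).
- Only the peer arm clustered: 5.0 / 5.9 / 6.7% and 5.4 / 7.2 / 9.2%.
- One fully nested SAFE arm vs control: 5.2 / 5.9 / 6.9% and 5.5 / 7.1 / 9.3%.
- Facilitators balanced across both SAFE arms, with no arm-specific variation: 4.0 to 4.9% for peer vs staff, so no inflation.

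Recruitment Methods in section 9 instead gives 120 with ASD plus 120 with IDD. Less 20% that is 192, or 64 per arm. The fully nested figures are then the same to within about 0.1 percentage point.

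**4. Which cluster sizes are plausible?** Section 9(b) puts SAFE delivery in years two and three. With even accrual (an assumption), 40/24 ≈ 1.7 people join each arm per month. A same-arm group of 4 takes 4/1.67 ≈ 2.4 months to fill and a group of 8 about 4.8 months, against a course of 2 to 4 weeks. At 80 per arm these times halve. A group formed from one randomisation block has at most 4 per arm. Training groups of 2 to 4 are therefore more natural than 8, and the clusters-of-8 row mainly describes a facilitator caseload, which the documents neither state nor exclude.

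**The case against.** The strongest reply is that the problem may be small or absent. Individual delivery is allowed, sessions are arranged at each participant's convenience, and the staff arm can be read as each participant's own support worker teaching only that person. At the implied accrual, groups of 2 are quite possible, and there the ANOVA error is at most about 6%. The project is also framed partly as proof of concept. All of this stands, and it limits the size of the point. It does not remove it: group delivery is a stated option, the peer arm could be clustered even if the staff arm is not, and question 3 has no other stated test.

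A second reply is that the remedy is imperfect. At ICC 0.01 with clusters of 4 to 8, a mixed model with its variance component bounded at zero runs at about 3.4 to 3.7%, further from 5% than the ANOVA's 5.3 to 5.9%. With two clusters per arm it reaches about 7% at ICC 0.10. The check also covered only a balanced peer-vs-staff layout, without singletons or unequal clusters. This stands too, and argues for a simple model with the ANOVA shown beside it.

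A reader might infer that the trial's error rate is in fact 9 to 13%. The documents do not support that: it needs clusters of about 8 and an ICC of 0.05 or more, and neither is given.

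**Conclusion.** The point holds conditionally. The plan permits shared groups and arm-specific facilitators and has no provision for them. If sharing occurs and the ICC is positive, the ANOVA standard error for peer vs staff is too small by about √DE.

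Over clusters of 2 to 4 and ICC 0.01 to 0.10, the nominal 5% becomes about 5 to 8.7% with both SAFE arms fully nested. Facilitator caseloads of 8 would take it to 5.9 to 13.3%. With partial sharing and an ICC of 0.01 the effect is negligible. It is nil for peer vs staff with unshared one-to-one delivery, or with facilitators balanced across the SAFE arms and no arm-specific variation.

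Two further inferences go too far. The ANOVA is not wrong whatever the delivery format; if nothing is shared it can stand on this point. Nor does this point bear on baseline adjustment, which is a separate matter.

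The change should be made because it is cheap and because IDs not recorded at delivery may not be recoverable. Confidence is medium, since cluster size, share taught in groups, caseload and ICC are all unstated.

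**What to change.** 1. Record a training-group ID and a facilitator ID for every SAFE participant, and state whether a facilitator may work in both SAFE arms.
2. In Data Analysis, pre-specify that if groups or arm-specific facilitators are shared, peer vs staff and SAFE vs control use a partially nested linear mixed model (SPSS MIXED, Satterthwaite df). Use one random intercept for the highest shared level in the SAFE arms, with controls and unshared participants as singletons. If nothing is shared, the planned ANOVA stands.
3. If facilitators work in both SAFE arms, add a facilitator-by-arm term only if it can be estimated.
4. Report the number of groups and facilitators per arm and the ICC, and show the ANOVA alongside.
5. Label peer vs staff exploratory if there are very few clusters per arm (for example two).

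**Cost.** Two data fields and a conditional paragraph; no extra participants or staff. Where sharing occurs, intervals widen. With 32 per arm, the independent 95% half-width is 1.986 × √(2/32) = 0.50 SD. At an assumed ICC of 0.05, the simulated mean half-width under the mixed model is about 0.58 SD with eight clusters per arm, 0.69 SD with four and 1.19 SD with two. The test is also conservative at low ICC, as described above.
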